A phase 3 study, PALOMA-2 (Finn et al, 2016), was conducted with 666 post-menopausal women without prior systemic therapy for ER+/HER2– ABC. Patients were randomized to a 2:1 ratio to receive palbociclib + letrozole or placebo + letrozole. The median PFS was 24.8 months with palbociclib + letrozole and 14.5 months with placebo + letrozole (HR=0.58; 95% confidence interval [CI] 0.46, 0.72, $P<0.000001$). Common adverse events (AEs; all grades) with palbociclib + letrozole vs placebo + letrozole were neutropenia (75% vs 5%), fatigue (41% vs 23%), nausea (25% vs 13%), arthralgia (33.3% vs 33.8%), and alopecia (32.9% vs 15.8%). Grade 3/4 neutropenia occurred in 54% of patients; other AEs were of Grade 1 severity. Febrile neutropenia was seen only with palbociclib + letrozole (2.5%). Permanent discontinuation due to AEs occurred in 9.7% of patients receiving palbociclib + letrozole vs 5.9% receiving placebo + letrozole. PALOMA-2 confirmed the significant clinical benefit and safety of palbociclib + letrozole in ER+/HER2– ABC patients who had not received prior systemic therapy for their advanced disease (Finn et al, 2016).

Another phase 3 study, PALOMA-3, was conducted with 521 patients with advanced HR+/HER2– patients that had relapsed or progressed during prior endocrine therapy (Turner et al, 2015). Patients were randomized to a 2:1 ratio to receive palbociclib + fulvestrant or placebo + fulvestrant. The median PFS was 9.2 months (95% CI, 7.5, upper limit not estimable) with palbociclib + fulvestrant and 3.8 months (95% CI 3.5, 5.5) with placebo + fulvestrant (HR for disease progression or death, 0.42; 95% CI 0.32, 0.56; $P<0.001$). The most common grade 3 or 4 AEs in the palbociclib+fulvestrant group were neutropenia (62.0%, vs. 0.6% in the placebo + fulvestrant group), leukopenia (25.2% vs. 0.6%), anemia (2.6% vs. 1.7%), thrombocytopenia (2.3% vs. 0%), and fatigue (2.0% vs. 1.2%). Febrile neutropenia was reported in 0.6% of patients in each treatment group. The rate of discontinuation due to AEs was 2.6% vs. 1.7% (Turner et al, 2015).

Estrogen receptor-positive breast cancer is biologically heterogeneous. Although palbociclib clinical trial results are very promising, it is also recognized that not all patients may respond to palbociclib treatment, and palbociclib treatment does come with mechanism based toxicities. **CCI**

[REDACTED]

[REDACTED]

[REDACTED]

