8.2.1. Inclusion Criteria

Patients must meet all of the following inclusion criteria to be eligible for enrollment into the study:

1. Age \geq 18 years or older.
2. Diagnosis of adenocarcinoma of the breast with evidence of metastatic disease or advanced disease not amenable to treatment with curative intent.
3. Documented HR+ (ER+ and/or PR+) tumor based on local standards.
4. Documented HER2- tumor based on local standards.
5. Physician has determined that treatment with palbociclib is indicated.
6. Evidence of a personally signed and dated informed consent document indicating that the patient has been informed of all pertinent aspects of the study.

7. Patients who in the opinion of the investigator are willing and able to comply with regular clinic visits as per standard of care practice at the site.

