Overall palbociclib treatment will be summarized as below for the FAS overall and by LOT:

- Number of cycles of palbociclib received
- Length of palbociclib treatment (months)
- Treatment disposition: (still receive palbociclib, discontinued palbociclib)

Palbociclib prescribing and treatment patterns will also be explored by cycle. For each cycle, below will be summarized:

- Starting dose (if less than 125mg, present reason)
- Primary reason for selecting palbociclib for the first cycle
- Dose modification (type, dose received after modification, reason)

Treatment patterns following enrollment will be reported, which include only lines started at enrollment:

- Type of therapy received (such as chemotherapy, hormonal therapy, other therapy)
- Agent (drug) composition of the treatment regimen received
- Time from initiation of treatment to initiation of each subsequent lines of treatment

- Time from discontinuation of previous line to initiation of the subsequent line of treatment
- Time from the start to end of each treatment line (in months for the total duration). This measure will be presented overall and by the top four regimens received in the line.

The sequence of agents/combination regimens received for first-line treatment in the ABC/MBC setting and subsequent lines of treatment will be presented. The proportion of all patients with each unique sequencing pattern will be reported for the overall study sample. Type of therapy sequencing (e.g., endocrine only, chemotherapy only, endocrine therapy combined with target therapy) will also be presented in the same format.

CLINICAL OUTCOMES

rwTR, rwPFS, and OS will be assessed by LOT (1st line, \geq 2nd line) in the ABC/MBC setting for the FAS. Based on the nonrandomized, observational nature of the study design, no clinical endpoints will be separately assessed and compared between specific treatment regimens.

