Real-world tumor response (complete response, partial response, stable disease, progressive disease) is determined by physician based on imaging, biopsies, biomarkers, and/or clinical judgment. Response as assessed by Response Evaluation Criteria in Solid Tumors (RECIST) criteria may not be available for all patients. rwTR will be derived as the best tumor response recorded from the palbociclib combination treatment start date until the first documentation of progressive disease. Only response assessments recorded on or before the start date of next subsequent line of treatment will be considered. The proportion of patients with a best response of complete response, partial response, stable disease, and progressive disease will be calculated and reported. Real-world response rate is defined as the proportion of patients with a best tumor response of complete response or partial response. Best tumor response, clinical benefit, and study end date are defined in Appendix 1 Data Derivation Details.

rwPFS will be estimated by LOT in the ABC/MBC setting. rwPFS is defined as time (months) from initiation of the palbociclib combination treatment to the earliest of clinician-documented progression or death due to any cause, whichever occurs first. Patients absent of the above events will be censored at the last date of response assessment without progressive disease.

OS will be estimated by LOT in the ABC/MBC setting. OS is defined as time (months) from initiation of the palbociclib combination treatment to date of death due to any cause. Patients do not have a documented death will be censored at last available visit date known to be alive.

Follow-up time will be calculated as time (months) from initiation of the palbociclib combination treatment to date of death or last available visit date. Median follow-up time and range (minimum, maximum) will be provided overall and by LOT.

Time-to-event outcomes (i.e., rwPFS, OS) will be analyzed using the Kaplan-Meier method and estimated survival curves will be displayed when appropriate. The number of patients at risk over time will be presented. A summary table will include number of patients with events, number of patients censored, and Kaplan-Meier quartiles (when estimable) accompanied by two-sided 95% confidence intervals (CIs). Based on the Kaplan-Meier life table, Survival function estimates at the specific time points (eg, 6, 12, 18, 24, 30 and 36 months) will also be reported along with two-sided 95% CIs.

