APPENDIX 1: DERIVED DATA DETAILS

Study End Date: the earliest of study withdrawal date or last contact visit date

Study Duration: defined in days as study end date minus baseline date +1.

Study Day: post-baseline visit or event date minus baseline date +1. For pre-baseline visits or events, study day is defined as pre-baseline visit or event date minus baseline date. Note there is no study equal to 0.

Age at baseline: defined in years as baseline date minus date of birth +1 divided by 365.25.

Duration of disease: defined in days from initial diagnosis date to study enrollment date.

Duration of ABC/MBC disease: defined in days from ABC/MBC diagnosis date to study enrollment date.

Disease-free interval: time from the end of adjuvant/neoadjuvant treatment to the first disease recurrence.

Paloma-3 disease-free interval: defined in days as the time between first diagnosis of breast cancer and onset of metastatic disease or disease recurrence.

Treatment-free interval: defined in days as the time from last dose of prior chemotherapy to first MBC therapy or first study dose whichever occurred earlier.

Line of Therapy (LOT):

Clinical outcome endpoints will be summarized by LOT which is defined based on the number of therapies taken after initial diagnoses of ABC or MBC, but before palbociclib treatment start:

- 1st line: patients had no LOT in the ABC/MBC setting before palbociclib initiation
- 2nd line: patients had one LOT in the ABC/MBC setting before palbociclib initiation
- 2⁺ line: patients had >1 LOT in the ABC/MBC setting before palbociclib initiation

Best Tumor Response: best overall tumor response recorded from palbociclib treatment start until first documentation of progressive disease. Only response assessments recorded on or before the start date of next subsequent line of treatment will be considered.

Clinical Benefit: a best overall tumor response of complete response or partial response at any time, or stable disease for at least 24 weeks post-study treatment initiation. Only response assessments recorded on or before the start date of next subsequent line of treatment will be considered.

Overall Survival (OS): is defined as time (months) from initiation of the palbociclib combination treatment to date of death, due to any cause.

First Hormonal Therapy After Stage III or IV Diagnosis: the first recorded MBC or adjuvant hormonal therapy after initial diagnosis of stage IIIb or IV MBC or ABC.

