Palbociclib Hormonal Partner: the concurrent hormonal therapy recorded while on Palbociclib. If the patient took both LETROZOLE and ANASTROZOLE then the first hormone partner (chronologically) is assigned.

Time from Initiation of Treatment to Initiation of Each Subsequent Line of Treatment: defined in days by subtracting the date of treatment initiation from the date of initiation of each subsequent treatment line and adding 1.

Time from Discontinuation of Previous Line to Initiation of the Subsequent Line of Treatment: defined in days by subtracting the initiation date of the previous line from the initiation date of the subsequent line and adding 1.

Time from the Start to End of Each Treatment: defined in months by subtracting the discontinuation date from the initiation date for each treatment line, adding 1, and then dividing by 30.4.

Charlson Comorbidity Index:

Assign a point score to each condition per Table 5 below. Point scores are then summed within patient to generate an overall score of disease burden.

Table 5: List of Comorbidities Collected at Time of Enrolment

Condition	Point Score
Charlson Comorbidity Index conditions:	
Cerebrovascular disease	1
Chronic pulmonary disease	1
Congestive heart failure	1
Connective tissue disease	1
Dementia	1
Diabetes with end organ damage	2
Diabetes without end organ damage	1
Depression	1
Hemiplegia or paraplegia	2
History of myocardial infarction	1
HIV/AIDS ^[a]	6
Hypertension	1
Mild liver disease	1
Moderate to severe liver disease	3
Use of warfarin	1
Moderate to severe renal disease	2
Peptic ulcer disease	1
Peripheral vascular disease	1
Skin ulcers/cellulitis	2
Other specific comorbidities	
Leukemia	N/A
Lymphoma	N/A
Neutropenia	N/A
Anemia	N/A
Other comorbidities not listed above	N/A
No comorbidities	N/A

[a] AIDS = acquired immune deficiency syndrome; HIV = human immunodeficiency virus.

PFIZER CONFIDENTIAL

ECOG Performance Scale:Developed by the Eastern Cooperative Oncology Group, [name], Group Chair.*

Grade	ECOG PERFORMANCE STATUS
0	Fully active, able to carry on all pre-disease performance without restriction
1	Restricted in physically strenuous activity but ambulatory and able to carry out work of a light or sedentary nature, e.g., light house work, office work
2	Ambulatory and capable of all selfcare but unable to carry out any work activities; up and about more than 50% of waking hours
3	Capable of only limited selfcare; confined to bed or chair more than 50% of waking hours

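### The SAP does not say what makes a line of therapy: read literally, an endocrine partner started shortly before palbociclib counts as a prior line and puts first-regimen patients into the ≥2nd line results

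*SAP*

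**What the plan says.** The lead sentence under Line of Therapy in SAP Appendix 1 says that LOT is "defined based on the number of therapies taken after initial diagnoses of ABC or MBC, but before palbociclib treatment start". The categories follow from it: "1st line: patients had no LOT in the ABC/MBC setting before palbociclib initiation" and "2nd line: patients had one LOT in the ABC/MBC setting before palbociclib initiation". A further category covers more than one prior LOT.

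The same appendix defines the hormonal partner as "the concurrent hormonal therapy recorded while on Palbociclib". It sets no condition on when that therapy started.

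Under Clinical Outcomes in SAP Section 8, "rwTR, rwPFS, and OS will be assessed by LOT", in two strata: 1st line and ≥2nd line. rwPFS is "time (months) from initiation of the palbociclib combination treatment to the earliest of clinician-documented progression or death due to any cause". LOT also splits palbociclib exposure (Study Drug Exposure), follow-up time, the EORTC QLQ-C30 comparisons (Section 8.9.1) and the neutropenia analyses (Section 8.9.6).

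Protocol Section 8.2.1 requires that "Physician has determined that treatment with palbociclib is indicated". No eligibility criterion concerns the start date of the endocrine partner, and Protocol Section 8.1 leaves treatment decisions to the physician and patient.

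**The concern.** Nothing in either document requires palbociclib and its endocrine partner to start together. Take a patient with newly diagnosed metastatic disease who starts letrozole and has palbociclib added three weeks later, with no progression in between. Under the lead sentence this patient has taken one therapy between diagnosis and palbociclib start, so the stratum is 2nd line. Under the partner definition the same letrozole course is also the palbociclib partner. One course of one drug is then both the prior line and part of the current one.

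No passage resolves this. There is no start window for the agents of a combination, no requirement that an earlier therapy has ended or failed before it counts as a line, and no exception for a drug that continues as the partner.

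The error would run in one direction. Patients on their first regimen for advanced disease move into ≥2nd line, and none move the other way. If they do better than true later-line patients, the ≥2nd line estimates look better than they should. The study is descriptive, so by-line estimates of this kind are among its main products.

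**Working it through.** **Reading the definitions together**

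1. The lead sentence counts therapies and anchors the count at palbociclib start. It does not anchor it at the start of the regimen that contains palbociclib.
2. The categories count LOT, a term that only the lead sentence defines.
3. The partner definition requires concurrency alone, so a partner with an earlier start still qualifies.
4. Eligibility does not remove these patients.

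Taken literally, 1–4 put the lead-in patient in ≥2nd line.

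**Partial dates**

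SAP Section 7 sets a missing day to the 15th, and a missing day and month to 30 June, for prior-therapy dates. Other start dates go to the first of the month or to 1 January. A partner begun on the same day as palbociclib but recorded by month only can therefore be dated before it: by up to about 30 days under the first-of-month rule, and by up to about two weeks under the 15th rule. A lead-in can thus appear in the data where none occurred. Which rule applies depends on whether the partner is treated as prior therapy, and that is the very question left open.

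**Illustrative size**

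The plan states no figure that depends on this definition, so there is none to reproduce.

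Inputs from Protocol Section 6.2:
- First-line median m1 = 24.8 months ("The median PFS was 24.8 months with palbociclib + letrozole and 14.5 months with placebo + letrozole"), with 20.2 months from the phase 1/2 study as an alternative.
- Later-line median m2 = 9.2 months, from the palbociclib plus fulvestrant arm of the trial in patients who had relapsed or progressed during endocrine therapy.

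Assumptions not in the documents:
- True first-line share f = 0.70.
- Share p of first-line patients whose partner started early, 5–20%.
- Exponential PFS.
- Lead-in patients share the prognosis of other first-line patients.

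Share of true first-line patients in the ≥2nd line stratum: w = f·p / (f·p + 1 − f)

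- p = 5%: 0.035 / 0.335 = 0.104
- p = 15%: 0.105 / 0.405 = 0.259
- p = 20%: 0.140 / 0.440 = 0.318

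Survival in the mixed stratum: S(t) = w·exp(−ln2·t/m1) + (1 − w)·exp(−ln2·t/m2). The median solves S(t) = 0.5.

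| p | w | Median, m1 = 24.8 | 12-month rwPFS, m1 = 24.8 | Median, m1 = 20.2 |
|---|---|---|---|---|
| 0 | 0 | 9.2 | 40.5% | 9.2 |
| 5% | 10.4% | 10.0 | 43.7% | 9.9 |
| 15% | 25.9% | 11.5 | 48.5% | 11.0 |
| 20% | 31.8% | 12.1 | 50.4% | 11.5 |

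Check of one 12-month value (p = 5%, m1 = 24.8): 0.104 × 0.715 + 0.896 × 0.405 = 0.437.

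The result depends on the assumed line mix. With f from 0.50 to 0.80 and p from 5% to 20%, w runs from about 5% to 44%. Because first line is assumed to be the larger group, a small lead-in share becomes a larger share of the smaller stratum.

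**The case against.** The strongest objection is that the misclassification is one reading and not the only one. The categories count LOT, and elsewhere the SAP treats a line as a regimen: Study Drug Exposure reports agents and combination regimens by line, and the rwPFS clock starts at the palbociclib combination. A programmer could fold an early-started partner into the palbociclib line, and the case report form, which is not in the documents, may decide how lines are entered. This stands, and it is why the point is limited to the literal reading. It does not remove the defect, since two programmers could derive different strata from the same text.

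Other parts of the objection also stand:

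- A reader might infer that LOT is the only split planned for clinical outcomes. It is not. SAP Section 5 (Subgroups) calls for assessment by hormonal partner and up to two further subgroups, and General Methods in Section 8 calls for summaries by treatment combination.
- A reader might take 24.8 against 9.2 months as the documents' own contrast between lines. The two trial populations also differ in endocrine partner and endocrine history, and both figures are trial PFS, not rwPFS. The 9.2 months has a 95% CI from 7.5 to not estimable, which contains every shifted median shown.
- A reader might infer that the treatment-sequence tables are distorted. The LOT definition is introduced for clinical outcome endpoints, and the sequence output lists agents and regimens, so letrozole followed by letrozole plus palbociclib would be visible there.
- The lead-in share and the line mix come from neither document.

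The descriptive purpose, with no formal hypothesis testing (Protocol Section 8.7), limits the consequences but does not make an unclear stratum acceptable.

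**Conclusion.** The concern holds as a gap in the definition. The literal rule places a patient with a continuing, early-started partner in ≥2nd line, and no passage says otherwise. This affects the ≥2nd line estimates of tumour response, rwPFS and OS, and the LOT splits of exposure and quality of life.

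The number of patients affected is unknown. Under the stated assumptions the ≥2nd line median would read 10.0–12.1 months instead of 9.2 (9.9–11.5 with the lower first-line median). These figures show direction and possible scale and are not a forecast. The documents do not support saying that the results will be wrong by this amount, or that lead-in is common. The point should be corrected because the rule can give the wrong stratum and the correction is small.

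**What to change.** In SAP Appendix 1:

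- Count prior lines as regimens, not as individual therapies.
- State that an endocrine agent belongs to the palbociclib line, and is not a prior line, if it started in the ABC/MBC setting within a pre-specified window before the first palbociclib dose, was still ongoing at that dose, and had no recorded progression or change of regimen in between.
- State how a patient is classified when the partner's start date is partial and imputed under Section 7.
- Tabulate the number of patients reclassified by the rule.
- Run sensitivity analyses with an alternative window and with the literal count.

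The rule changes only the stratum; the time origin for rwPFS and OS stays as defined. It should rest on recorded progression where available, because neither document specifies that progression dates on prior therapy are collected.

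The cost is a few sentences, one derivation from treatment dates, one table and two sensitivity runs. The downside is small: the window length (for example 60 days, with 28 days as the alternative) is an analysis convention with no clinical meaning, and the sensitivity runs show whether it matters.

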ANNEX 1. LIST OF STAND ALONE DOCUMENTS

- EORTC QLQ-C30 (version 3)
- G8 (Geriatric Screening Tool): POLARIS STUDY VERSION 1 26OCT2016
- ADL Activities of Daily Living: POLARIS STUDY VERSION 1 26OCT2016

EORTC QLQ-C30

ENGLISH

EORTC QLQ-C30 (version 3)

We are interested in some things about you and your health. Please answer all of the questions yourself by circling the number that best applies to you. There are no "right" or "wrong" answers. The information that you provide will remain strictly confidential.

Please fill in your initials:

--	--	--	--

Your birthdate (Day, Month, Year):

--	--	--	--	--	--

Today's date (Day, Month, Year):

31

--	--	--	--	--	--	--

	Not at All	A Little	Quite a Bit	Very Much
1. Do you have any trouble doing strenuous activities, like carrying a heavy shopping bag or a suitcase?	1	2	3	4
2. Do you have any trouble taking a long walk?	1	2	3	4
3. Do you have any trouble taking a short walk outside of the house?	1	2	3	4
4. Do you need to stay in bed or a chair during the day?	1	2	3	4
5. Do you need help with eating, dressing, washing yourself or using the toilet?	1	2	3	4

During the past week:

	Not at All	A Little	Quite a Bit	Very Much
6. Were you limited in doing either your work or other daily activities?	1	2	3	4
7. Were you limited in pursuing your hobbies or other leisure time activities?	1	2	3	4
8. Were you short of breath?	1	2	3	4
9. Have you had pain?	1	2	3	4
10. Did you need to rest?	1	2	3	4
11. Have you had trouble sleeping?	1	2	3	4
12. Have you felt weak?	1	2	3	4
13. Have you lacked appetite?	1	2	3	4
14. Have you felt nauseated?	1	2	3	4
15. Have you vomited?	1	2	3	4
16. Have you been constipated?	1	2	3	4

Please go on to the next page

ENGLISH

During the past week:	Not at All	A Little	Quite a Bit	Very Much
17. Have you had diarrhea?	1	2	3	4
18. Were you tired?	1	2	3	4
19. Did pain interfere with your daily activities?	1	2	3	4
20. Have you had difficulty in concentrating on things, like reading a newspaper or watching television?	1	2	3	4
21. Did you feel tense?	1	2	3	4
22. Did you worry?	1	2	3	4
23. Did you feel irritable?	1	2	3	4
24. Did you feel depressed?	1	2	3	4
25. Have you had difficulty remembering things?	1	2	3	4
26. Has your physical condition or medical treatment interfered with your family life?	1	2	3	4
27. Has your physical condition or medical treatment interfered with your social activities?	1	2	3	4

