8 STATISTICAL ANALYSIS

This study has a convenience sample; thus, results may not be generalizable to the entire population with the disease. Due to the study's exploratory nature, study measures will be summarized descriptively. Furthermore, any p value reporting should be placed in a descriptive framework for hypothesis generation and any such inferential analysis is intended to guide further research.

All analyses will be conducted using SAS® version 9.4 or higher.

The intention is to analyze all available data. In the advent that COVID may cause gaps in subject data or require adjustments to statistical methodologies, our intent is to address such issues if or as needed. Both ICON and Pfizer have internal guidances and recommendations on file to assist with decision-making with regards to COVID-related data issues and these will be consulted if or as needed.

GENERAL METHODS

For continuous variables, means, standard deviations (SD), medians, minimums, maximums, and missing will be reported. For discrete variables, frequencies and percentages will be reported. Missing or unknown categories for each variable also will be presented. Percentages will be calculated excluding missing or unknown values. 95% Confidence Intervals (CI) are two-sided.

All summaries will be performed for all patients in the corresponding analysis set and by treatment combination defined at study entry within the corresponding analysis set:

- Palbociclib + Letrozole or Anastrozole
- Palbociclib + Fulvestrant
- Palbociclib + Exemestane
- Other

The baseline record is defined as the last observed measurement prior to palbociclib administration. Change from baseline is defined as the post-baseline value minus the baseline value.

Time in days between two dates will be calculated using the formula most recent date minus earlier date plus 1. For time in months, the same formula for days will be applied but then divided by 30.4. For time in years, the same formula for days will be applied but then divided by 365.25.

Variable definitions are found in Appendix 1 Data Derivation Details.

DISPOSITION OF SUBJECTS

A subject disposition summary will be reported. Subjects' study completion date and reason for premature termination will be reported in listing format. Number of subjects with initial diagnosis and with recurrent diagnosis will be reported in table and listing format.

DEMOGRAPHIC AND BASELINE CLINICAL CHARACTERISTICS

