4	Completely disabled; cannot carry on any selfcare; totally confined to bed or chair
5	Dead

EORTC QLQ-30 Scoring:

15 scales and items are calculated per Table 6 below.

Table 6: EORTC QLQ-30 Scoring Instructions

Scale/Item Label	Scale Name	Item Number	Raw Score (RS) ^[a]	Score
Global health status/QoL	QL2	29, 30	$(I_{29} + I_{30}) / 2$	$[(RS - 1) / 6] * 100$
Physical functioning	PF2	1 to 5	$(I_1 + I_2 + I_3 + I_4 + I_5) / 5$	$[1 - (RS - 1) / 3] * 100$
Role functioning	RF2	6, 7	$(I_6 + I_7) / 2$	$[1 - (RS - 1) / 3] * 100$
Emotional functioning	EF	21 to 24	$(I_{21} + I_{22} + I_{23} + I_{24}) / 4$	$[1 - (RS - 1) / 3] * 100$
Cognitive functioning	CF	20, 25	$(I_{20} + I_{25}) / 2$	$[1 - (RS - 1) / 3] * 100$
Social functioning	SF	26, 27	$(I_{26} + I_{27}) / 2$	$[1 - (RS - 1) / 3] * 100$
Fatigue	FA	10, 12, 18	$(I_{10} + I_{12} + I_{18}) / 3$	$[(RS - 1) / 3] * 100$
Nausea and vomiting	NV	14, 15	$(I_{14} + I_{15}) / 2$	$[(RS - 1) / 3] * 100$
Pain	PA	9, 19	$(I_9 + I_{19}) / 2$	$[(RS - 1) / 3] * 100$
Dyspnea	DY	8	I_8	$[(RS - 1) / 3] * 100$
Insomnia	SL	11	I_{11}	$[(RS - 1) / 3] * 100$
Appetite loss	AP	13	I_{13}	$[(RS - 1) / 3] * 100$
Constipation	CO	16	I_6	$[(RS - 1) / 3] * 100$
Diarrhoea	DI	17	I_7	$[(RS - 1) / 3] * 100$
Financial difficulties	FI	28	I_{28}	$[(RS - 1) / 3] * 100$

[a] "I" indicates item response value. Raw score (RS) is the average of all nonmissing item values if at least $\frac{1}{2}$ the item values comprising the scale are nonmissing. For instance, if I_3 and I_5 are missing but the other 3 item values comprising PF2 are nonmissing, RS is calculated as $(I_1 + I_2 + I_4) / 3$.

EORTC QLQ-30 Categories:

- (1) Worsening is defined as a change from baseline of at least a 10-point decrease in score on the functioning domains and global quality of life and at least a 10-point increase in score on the symptom items.
- (2) Improving/Maintaining is defined otherwise.

PFIZER CONFIDENTIAL

G8 Screening Tool²²⁻²⁴

An index (or total) score is calculated by assigning a score to each item per Table 7 below and summing all scores within patient. If any items are missing, the index score is missing. The score ranged from 0 (heavily impaired) to 17 (not at all impaired).

Table 7: G8 Screening Tool Index Score Calculation

	Items	Possible responses (score)

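### Three derivations in SAP Appendix 1 give the wrong quantity as written: the gap between lines, the duration of a line, and the constipation and diarrhoea scores

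*SAP*

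**What the plan says.** **Gap between lines.** SAP Appendix 1 defines a variable titled "Time from Discontinuation of Previous Line to Initiation of the Subsequent Line of Treatment". Its formula, in days, is "subtracting the initiation date of the previous line from the initiation date of the subsequent line and adding 1". SAP Section 8 (Study Drug Exposure) lists this variable among the treatment-pattern measures to be reported: "Time from discontinuation of previous line to initiation of the subsequent line of treatment". The definition just before it in Appendix 1, time from treatment initiation to the start of each later line, also runs from one start date to another, plus 1.

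**Line duration.** Appendix 1 has this "defined in months by subtracting the discontinuation date from the initiation date for each treatment line, adding 1", and then divided by 30.4. The general rule in SAP Section 8 (General Methods) is "Time in days between two dates will be calculated using the formula most recent date minus earlier date plus 1".

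**QLQ-C30 scoring.** In Appendix 1, Table 6, two rows read "Constipation CO 16 I_6" and "Diarrhoea DI 17 I_7" in the columns for scale, scale name, item number and raw score. The role-functioning row of the same table is built from items 6 and 7. The questionnaire in Protocol Annex 1 prints "6. Were you limited in doing either your work or other daily activities". Its item 7 asks about hobbies and leisure, item 16 about constipation and item 17 about diarrhoea.

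**The concern.** Appendix 1 is the controlling text. General Methods refers to it for variable definitions, and SAP Section 6 refers to it for the QLQ-C30 scoring algorithm. A program written faithfully from it would report something other than what the table titles say.

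Prescribing and treatment patterns are the stated primary goal (Protocol Section 8.1; SAP Study Design). Section 8 lists three line-timing measures, and two of them are affected. Duration is to be shown overall and by the four most common regimens in each line. The constipation and diarrhoea scores feed the visit summaries, paired t-tests, comparison with population norms, subgroup comparisons and worsening percentages in SAP Section 8.9.1. SAP Section 4 allows repeated interim analyses for abstracts and manuscripts, so an error could reach publication before the final analysis.

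**Working it through.** The plan states no numerical result here, so each formula is applied literally to illustrative inputs and compared with the variable's own name, the General Methods rule, or the Item Number column of Table 6.

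**Illustrative dates (assumed).** Previous line starts 1 January 2018 and stops 30 June 2019; next line starts 15 July 2019. Stop minus start is 545 days; next start minus previous start is 560 days; next start minus previous stop is 15 days.

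1. *Gap.*
   - As written: next start − previous start + 1 = 560 + 1 = **561 days**.
   - By the variable's name and the general rule: next start − previous stop + 1 = 15 + 1 = **16 days**.
   - The excess, 561 − 16 = 545 days, is exactly the previous line's stop minus start. The error therefore grows with time on the previous line.

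2. *Duration.*
   - As written: (start − stop + 1)/30.4 = (−545 + 1)/30.4 = **−17.89 months**.
   - By the general rule: (545 + 1)/30.4 = **+17.96 months**.
   - In general, with k = stop − start in days, the written formula gives (1 − k)/30.4. That is 1 day at k = 0, zero at k = 1 and negative from k = 2. At k = 365 it gives −11.97 months against +12.04.
   - Dropping the minus sign is not a repair. The +1 then works the wrong way, and the result is 544 days instead of 546.

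3. *QLQ-C30.* Each single-item symptom score is (RS − 1)/3 × 100. Assume a patient with no role limitation (I_6 = 1, I_7 = 1), severe constipation (I_16 = 4) and marked diarrhoea (I_17 = 3).
   - Constipation as written, from I_6: (1 − 1)/3 × 100 = **0**. From I_16: (4 − 1)/3 × 100 = **100**.
   - Diarrhoea as written, from I_7: **0**. From I_17: (3 − 1)/3 × 100 = **66.7**.
   - Role functioning is [1 − ((I_6 + I_7)/2 − 1)/3] × 100. Substituting the two written symptom scores gives role functioning = 100 − (constipation + diarrhoea)/2. This holds for all 16 response combinations, so the two bowel scores would add nothing to what role functioning already reports.
   - Scales affected: 2 of 15 = 13%.

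**The case against.** The best case for the plan is that a competent programmer would correct all of this without being told.

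- *Duration.* The general rule gives the right direction, the variable's name fixes start and end, and a table of negative durations would be noticed at once. This largely stands: silent corruption is unlikely for this variable. The specific definition still contradicts the general one.
- *QLQ-C30.* The Item Number column shows 16 and 17, and the table's footnote defines the raw score as the mean of the items in the scale. A programmer working from that column scores correctly. This also stands, but the adjacent column gives an explicit formula that says otherwise, and the wrong scores would lie between 0 and 100 and look valid. The table was read from PDF by a program, so a lost digit cannot be fully excluded. The neighbouring single-item rows kept both digits (I_11, I_13, I_28).
- *Gap.* Only the variable's name points to the right date. The general rule does not help, because the formula names the wrong date, and the output is positive and plausible.

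Three limits on scope are fair. The gap formula certainly duplicates the start-to-start variable only for the first subsequent line; beyond that it depends on which start date the other variable uses. Treatment sequence is an objective separate from the primary goal, and its summary of regimens uses neither formula. The study is descriptive, with no formal hypothesis testing planned.

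None of this makes the written formulas right. A programmer who corrects them departs from the SAP without a record, and an independent validator working from the SAP would not match.

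**Conclusion.** All three definitions are wrong as written. The gap is overstated by the full length of the previous line (561 days instead of 16 in the example). Duration has the wrong sign for any line whose dates differ by two days or more, and its absolute value is then two days short. Two of 15 QLQ-C30 scores measure role limitation under bowel-symptom labels. The gap formula is the most serious, because nothing in its output would reveal it.

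The sizes rest on the assumed dates and responses; the direction and form of each error do not. The documents do not show whether any program followed the text literally. Real-world progression-free survival, overall survival, tumour response and the sample size do not use these formulas.

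**What to change.** In SAP Appendix 1:

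1. Gap = initiation date of the subsequent line − **discontinuation** date of the previous line + 1.
2. Line duration in months = (discontinuation date − initiation date + 1)/30.4.
3. Table 6 raw scores: constipation = I_16, diarrhoea = I_17.

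Keeping the +1 in the gap follows the General Methods rule. State its consequence beside the definition: a next line started the day after discontinuation counts as 2 days, and the 15-day difference in the example counts as 16.

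Check existing programs against the corrected definitions, and re-run any interim output found to have used the old ones. The cost is an SAP wording change and a programming check, with no new data.
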